- · The proposed sample composition of subjects.

You may reference grant application/sponsor's relevant protocol pages and attach as an appendix using the below attachment button, however, a summary paragraph must be provided in the text box below.

Proposed dates of enrollment: November 1st, 2020 to December 31st, 2021

The trial will be conducted in Iquitos, Peru. Patients will be recruited from the community, local health-care clinics, and post-secondary educational institutions through word-of-mouth, active recruitment by study staff, and self-referral in response to advertisements. Verbal permission will be sought at private locations where advertisements will be posted, and a signed letter of authorization will be obtained from any performance site where recruitment activities take place. Men and women between the ages of 18 and 70 years with P. falciparum or P. vivax malaria monoinfection living in Peru. 2-6 cohorts of adult patients (10 patients per cohort) with acute,

53333

uncomplicated P. falciparum or P. vivax malaria monoinfection. In total, there will be a minimum of 20 and a maximum of 60 patients. In general, the people who live in these recruitment areas are representative of the general population that suffers malaria in the Amazon region. They are generally mestizo and do not live in extreme poverty. Their educational level includes completion of primary or high school.

Inclusion Criteria:

1) Male or female, aged 18 to 70 years of age (inclusive) at screening.

2) Body weight between 45 kg and 90 kg inclusive

3) Presence of mono-infection of P. falciparum or P. vivax confirmed by:

a. Fever, as defined by axillary temperature = 37.5°C or oral/rectal/tympanic temperature = 38°C, or history of fever in the previous 24 hours (history of fever must be documented) and,

b. Microscopically confirmed parasite infection: 1,000 to 40,000 asexual parasite count/µL blood

4) Written informed consent provided by participant, in accordance with local practice. If the participant is unable to write, witnessed consent is permitted according to local ethical considerations.

5) Ability to swallow oral medication.

6) Ability and willingness to participate and to comply with the study requirements

7) Agreement to hospitalization for at least 102 hours and/or until malarial parasites are not detected by microscopy on 2 consecutive occasions.

8) Agreement to come back to the hospital on Days 7, 10 or 11, 14, 17 or 18, 21, 24 or 25, 28, 35, and 42.

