
9) Women of child-bearing potential, has a negative pregnancy test at screening, and agrees to comply with one of the following during the treatment stage of the study and for a period of 30 days after stopping study drug:

a. Use of oral, implantable, or injectable hormonal contraceptive, either combined or progestogen alone used in conjunction with barrier method as defined below.

b. Use of an intrauterine device with a documented failure rate of <1% per year.

c. Barrier method consisting of either condom or diaphragm.

d. Male partner who is sterile prior to the female subject's entry into the study and is the sole sexual partner for that female.

e. Complete abstinence from intercourse for 2 weeks prior to administration of study drug, throughout the study and for a period of 30 days after stopping study drug.

Exclusion Criteria:

1) Signs and symptoms of severe/complicated malaria according to the World Health Organization Criteria 2010 (Attachment 1: Definition of Severe Malaria)

2) Mixed Plasmodium infection.

3) Severe vomiting, defined as more than three times in the 24 hours prior to inclusion in the study, or severe diarrhea defined as 3 or more watery stools per day.

4) Severe malnutrition (defined as the weight-for-height being below -3 standard deviation or less than 70% of median of the NCHS/WHO normalized reference values)

5) Presence of a significant medical or psychiatric condition, or any other serious or chronic clinical condition requiring hospitalization, or any other condition that in the opinion of the investigator precludes participation in the study.

6) Female patients must not be either lactating or pregnant as demonstrated by a negative serum point-of-care pregnancy test predose (the result of the pre-dose assessment must be confirmed negative prior to dosing).

7) Employment under the direct supervision of the investigators or study staff.

8) Clinically significant alterations to hematologic or clinical chemistry parameters that in the opinion of the investigator precludes participation in the study, including:

a. AST/ALT > 3 x upper limit of normal range (ULN) and total bilirubin is normal

b. AST/ALT > 2 x ULN and total bilirubin is >1 and <1.5 x ULN and conjugated bilirubin is > 35% of the total bilirubin

c. Total bilirubin > 1.5 x ULN

d. Serum creatinine levels > 2 x ULN

e. Hb level < 8 g/dL

f. Platelet level < 50,000/mm3

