• Proportion of patients with a decrease in hemoglobin (Hb): > 2 g/dL from baseline to an absolute value of < 5 g/dL

- Proportion of patients with an absolute Neutrophil count $< 1,000/\mu$ L after baseline
- Proportion of patients meeting Hy's law criteria
- Proportion of patients with the following LFT changes:
 - Any ALT or $AST \ge 5 \times ULN$
 - Any AST or ALT ≥ 3 x ULN together with the appearance of fatigue, nausea, vomiting, right upper quadrant pain or tenderness, fever, rash and/or eosinophilia (eosinophil percent or count above the ULN)
 - Persistent ALT $\ge 3 \text{ x}$ ULN for a period of more than 4 weeks.

• Proportion of patients with clinical signs of possible cutaneous adverse reactions such as dermatitis, rash, erythematous rash, macular rash, papular rash, maculo-papular rash, pruritic rash, pustular rash, vesicular rash

• Proportion of patients with clinically significant increases in venous methemoglobin levels

• Proportion of patients with significant changes in ECG findings, including heart rate, ECG intervals (PR, QTcB, QTcF), conduction changes or abnormalities

Success criterion: No repeated drug-related serious adverse events (Attachment 3, Section 8.1.2).

Secondary Endpoints

Secondary endpoints related to malaria signs and symptoms up to Day 42

- Proportion of patients with symptoms or physical examination signs related to uncomplicated *P. vivax* or *P. falciparum* malaria (dizziness, headache, nausea, anorexia, vomiting, diarrhea, pruritus, urticaria, skin rash, abdominal pain, joint pain, muscle pain, palpitations, sleep disturbance, confusion, hearing disturbance, visual disturbance, fatigue)
- Fever Clearance Time as defined as the time from baseline to the first of two consecutive post-dose axillary temperature measurements < 37.5°C obtained within an interval of 4 to 24 hours of each other.

Secondary endpoints related to secondary treatment outcomes

- Crude ACPR at Days 28, 35, and 42 (*P. vivax* or *P. falciparum*)
- Recurrence (*P. vivax* or *P. falciparum*) up to Day 42

Secondary endpoints related to parasite clearance kinetics by microscopy

- Parasite clearance time (PCT)
- PRR (parasite reduction rate) and parasitemia half life
- Times to microscopic clearance of asexual parasites
 - Total reduction (PC100)
 - 99% reduction (PC99)
 - 90% reduction (PC90)
 - 50% reduction (PC50)
- Microscopically determined percentage reduction in asexual parasites from baseline at:

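### The primary safety endpoint for neutrophils below 1,000/µL has no baseline condition, so a patient who enters low and stays low counts as an event

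*Combined protocol and SAP*

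**What the plan says.** SAP Section 3 (Data Elements, primary endpoints related to safety and tolerability) lists "Proportion of patients with an absolute Neutrophil count" under 1,000/µL after baseline. The bullet directly above it, for hemoglobin, is written differently and needs a fall of "> 2 g/dL from baseline to an absolute value of < 5 g/dL".

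Exclusion criterion 8 (IRB application, Study Population) opens with "Clinically significant alterations to hematologic or clinical chemistry parameters that in the opinion of the investigator precludes participation in the study, including" and then gives limits for transaminases, bilirubin, creatinine, hemoglobin and platelets. There is no figure for neutrophils.

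SAP Section 4 (General Approach) defines baseline as the last observation before study medication.

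The same Section 3 list has a liver line under LFT changes: AST or ALT of at least 3 x ULN "together with the appearance of fatigue, nausea, vomiting, right upper quadrant pain or tenderness, fever, rash and/or eosinophilia". Criterion 8a excludes "a. AST/ALT > 3 x upper limit of normal range (ULN) and total bilirubin is normal". Inclusion criterion 3a requires current fever or documented fever in the preceding 24 hours.

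**The concern.** The words after baseline say when the count is taken. They do not say that the count must be new or lower than before. With no numeric entry limit, the endpoint can include patients whose low count preceded SJ733. Every cohort receives SJ733, so no untreated group shows how many such patients to expect. In arms of 10, one patient is enough to change how the line reads.

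The measure is also one that readers will look at. The Potential Risks section of the IRB application reports a low leukocyte count as one of only two Phase 1a adverse events judged possibly related to SJ733.

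A smaller ambiguity affects the liver line. Fever or recent fever is a condition of entry. Fatigue, nausea, vomiting and rash also appear in the SAP's own list of malaria symptoms. If *appearance* were read as mere presence, the illness itself would supply the symptom half.

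**Working it through.** The plan states no figure for this endpoint, so there is nothing to reproduce. The check compares the rules and then sizes the effect of one patient.

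**1. Neutrophils against hemoglobin.**

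| | Entry limit | Change from baseline required |
|---|---|---|
| Hemoglobin | excluded below 8 g/dL | yes, more than 2 g/dL, to below 5 g/dL |
| Neutrophils | none stated; investigator judgement | no |

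A patient at the hemoglobin entry limit must lose more than 8 − 5 = 3 g/dL to be counted, so a low entry value alone can never make an event. For neutrophils, take a patient at 900/µL before dosing and 900/µL at each later visit. No numeric criterion excludes this patient, every later value is below 1,000/µL, and the patient is an event with no change at all.

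**2. Size of one such patient.** The contribution is 1/n.
- Arm of 10: 1/10 = 10 percentage points.
- Dose cohort of 20 (both parasite arms pooled, as the SAP's sample size section states): 1/20 = 5 percentage points.

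**3. How often it could happen.** The documents give no share of patients with baseline neutrophils below 1,000/µL. Call it p. The chance of at least one such patient among n is 1 − (1 − p)^n.

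| Assumed p | n = 10 | n = 20 |
|---|---|---|
| 1% | 1 − 0.99^10 = 10% | 1 − 0.99^20 = 18% |
| 5% | 1 − 0.95^10 = 40% | 1 − 0.95^20 = 64% |
| 10% | 1 − 0.90^10 = 65% | 1 − 0.90^20 = 88% |

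These show the range over assumed values of p. They are not estimates for this population, and each such patient counts only if at least one later value is also low.

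**4. With a baseline condition.** If one patient starts low and nobody else becomes low, the line changes from 1/20 (5%) to 0/19, or from 1/10 (10%) to 0/9.

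**5. Liver line: can the transaminase half be met at entry?** Criteria 8a to 8c were applied together.
- Normal bilirubin: 8a excludes values above 3 x ULN, so only a value of exactly 3.0 x ULN enters.
- Bilirubin above 1 and below 1.5 x ULN: 8b excludes values above 2 x ULN if the conjugated share exceeds 35%. Values of 3 x ULN or more can enter only with a conjugated share of 35% or less.
- Bilirubin exactly 1.5 x ULN: not covered by 8b or 8c.
- Bilirubin above 1.5 x ULN: excluded by 8c.

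The numeric limits therefore leave only narrow routes, each still subject to investigator judgement. For nearly all patients this line needs a transaminase rise after dosing. What stays open is the meaning of *appearance*.

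**The case against.** The strongest reply is that the plan already separates baseline disease from later findings. The Data and Safety Monitoring section treats conditions present at screening as baseline, and as adverse events only if they worsen. SAP Section 3 has a general laboratory endpoint that includes changes from baseline. SAP Section 5 plans a laboratory summary and a plot of neutrophils over time. An investigator may also exclude a clinically significant low count. With 10 patients per arm, a reviewer could see which low counts came before dosing.

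Part of this stands. The information will exist and the context can be recovered. But the screening rule governs adverse event reporting, the change-from-baseline wording belongs to another bullet, and investigator judgement does not guarantee exclusion at, say, 900/µL. None of these alters what the neutrophil proportion counts.

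A reader might go further and infer that the plan reports pre-existing disease as an effect of SJ733. The documents do not support that. The proportions are descriptive, and drug-relatedness is a separate endpoint rated by the investigator. Nor do they support the reading that patients routinely enter with AST/ALT of 3 x ULN or more, since criteria 8a to 8c close most of that route. The liver line also asks for symptoms that appear, under a heading of changes, which points towards new findings.

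**Conclusion.** The neutrophil endpoint, as written, can count a low value that was there before treatment and did not change. One such patient is worth 10 points in an arm of 10 or 5 points in a dose cohort of 20. Whether any patient will enter below 1,000/µL is unknown from the documents, so the expected effect rests wholly on an assumed prevalence.

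The consequence is limited to how a primary safety proportion reads in an uncontrolled trial. It might be thought to distort cohort decisions. Interim review does include laboratory data, but the safety success criterion and the progression guidelines rest on repeated drug-related SAEs and, for efficacy, on cure counts. Neither the neutrophil line nor the liver line is a trigger.

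The liver line needs only a definition of *appearance*. The point as a whole is an inexpensive improvement, not a flaw that invalidates the safety analysis.

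**What to change.** In SAP Section 3:

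- Count neutrophils below 1,000/µL after baseline only in patients whose baseline, as defined in SAP Section 4, is at least 1,000/µL, and state that denominator.
- Show patients below 1,000/µL at baseline in a shift table of baseline against lowest later value, so that nobody disappears from the report. Say where patients with no baseline value are shown.
- For the line combining AST/ALT of at least 3 x ULN with symptoms, state that *appearance* means a symptom that began or worsened after the first dose, judged against the malaria signs and symptoms recorded at baseline.

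The cost is SAP wording and some programming. Baseline hematology and malaria signs are already collected, so no new data are needed. The downside is a slightly smaller denominator for the neutrophil line, for example 19 instead of 20.

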- 7) Investigation New Drug administration (all cohorts will receive SJ733; cohorts 1 and 3 will also receive Cobicistat)
- 8) Study Completion information
- 9) ECG evaluation
- 10) Hematology; Blood chemistry; Urinalysis
- 11) Adverse Events tracking
- 12) Concomitant medication/ Significant non-drug therapies
- 13) Pharmacokinetic (PK) blood collection
- 14) Increased number of Parasitemia blood collection and assessment (microscopy/qPCR)
- 15) Parasite genetic assessments (to determine potential mechanisms of resistance)

STANDARD/ROUTINE CLINICAL CARE PROCEDURES

1) Single Physical examinations (body height, body weight, body temperature, blood pressure, pulse rate,)

53333

2) Single Pregnancy test

3) Concomitant medication/ Significant non-drug therapies

4) diagnostic Parasitemia determinations (microscopy/qPCR)

5) Administration of local standard drug therapy

Attachments

Attach Type	File Name
ResearchProcedures	20200406_SJ733_Clinical_Protocol_V1.0_en.docx

Data Collection: List the data or attach a list of the data to be collected about or from each subject (e.g. interview script, survey tool, data collection form for existing data).

If the research includes survey or interview procedures, the questionnaire, interview questions or assessment scales should be included in the application (use attachment button below).

The data collection instrument(s) can be submitted with your application in draft form with the understanding that the final copy will be submitted to the IRB for approval prior to use (submit final version to the IRB for review as a modification request if initial IRB approval was issued while the data collection instrument was in draft form).

Note: The IRB approval process does not include a statistical review. Investigators are strongly encouraged to develop data management and analysis plans in consult with a statistician.

Details regarding the data to be collected throughout the trial from screening to finalization can be found on pages 61 - 65 of the attached Clinical Protocol and include:

Written informed consent

Demographic data

· Medical and surgical history and details of current medical conditions

• Social history (including previous and current use of alcohol, tobacco products and drugs of abuse)

• Previous and concomitant medications (medications used currently and in the 28 days prior to screening will be recorded in the

- patient's CRF)
- Use of herbal products
- Signs and symptoms of malaria

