If success criteria for Cohort 1a are met, Cohort 2a will proceed with a lower exposure of SJ733. Likewise, if success criteria for Cohort 1b are met, Cohort 2b will proceed with a lower dose of SJ733. For the purposes of this decision, a-series cohorts (falciparum) will be treated independently from b-series (vivax) cohorts. If data from the first pair of cohorts do not meet the success criteria, but are inconclusive, the same dosing regimen may be repeated. The same approach will be used for progress from the second pair of cohorts to the third, but with the addition of the option to initiate a 3rd pair of cohorts, re-escalating SJ733 exposure by dosing the combination of SJ733 (300 mg) + cobicistat (150 mg) for three consecutive days. Established antimalarial therapy will be given if a patient meets any of the defined treatment failure criteria.

Dosing within a dose cohort will be paused if one serious adverse event (SAE; Section 8.1.2) is noted while determination of relatedness to study drug is being made. For a SAE, the decision of relatedness to study drug will ultimately be approved by the SRT and DSMB. The DSMB will determine if the nature of the event allows continuation. No additional subjects in the cohort will be dosed

if it is determined that the graded event meets the definition for stopping or if a second drug-related SAE is observed within that cohort.

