A minimum of one cohort containing two treatment arms (20 patients; 10 patients per arm) will be investigated with a maximum of 3 cohorts (60 patients; 3 dosing regimens; 2 arms; 10 patients per arm) being tested as shown in Figure 1. The starting dosing regimen for the first *P. vivax* or *P. falciparum* cohorts will be three consecutive daily doses of the combination of SJ733 (600 mg) and cobicistat (150 mg). Based on the results from completed Phase 1a/1b studies, this dose is expected to be well-tolerated and show complete clearance of parasites on Day 7 as determined by microscopy (thick blood smear) and a $\leq 20\%$ recrudescence rate as assessed by microscopy on Day 14.

If the data from the first cohorts of *P. falciparum* (cohort 1A) and *P. vivax* (cohort 1B) respectively meet the success criteria, two other dosing regimens, expected to yield reduced total exposures of SJ733, may be investigated. Each is expected to be efficacious. If data from the first cohorts are inconclusive, an adaptation will be triggered to use the same dosing regimen for a larger number of patients in order to improve statistical power and more accurately classify a potential failure. An inconclusive result will be defined at Day 14 as: 1) the absence of any repeated drug-related SAE; and 2) crude ACPR between 60-80% (equivalent to 20-40% recurrence). If data from the first cohorts result in failure, the trial will be stopped. Failure is defined as: 1) the detection of

any 2 incidents of the same drug-related SAE; or 2) crude ACPR < 60% (equivalent to > 40% recurrence).

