The overall study design is to demonstrate proof of concept and serves as an exploratory study. It is not intended to demonstrate superiority or non-inferiority against a control. Rather the goal is to establish preliminary data for planning future studies and to assess whether the SJ733 is safe and the observed curative rate equals or exceeds 80%. As such, there will be no statistical testing of hypotheses. This exploratory Proof of Concept study uses a fixed clinical safety and parasitological responses (primary endpoints) defined as the absence of any drug-related SAE or microscopically determined parasitemia 14-days after initiation of therapy in \geq 80% patients who did not violate any of the inclusion/exclusion criteria.

General Approach

The overall study design involves two cohorts receiving SJ733 doses (600 mg and 300 mg) with and without cobicistat (150 mg) as cohorts. Data subsets (eligible, evaluable and completer) will be used in the potential comparisons.

The primary analytic approaches will be descriptive. All data will be summarized descriptively for the appropriate analysis sets defined below: Continuous variables by descriptive statistics (number of patients [n], mean, standard deviation [SD], minimum, median, maximum); categorical data by absolute and relative frequencies (n and %) or contingency tables.

While this is a proof of concept, exploratory study, any potential comparisons between dose cohorts will be informative. Potential longitudinal data will be described as graphical summaries presented by each group. Unless indicated otherwise, summary statistics will be reported for observed data only, by dose cohort. Missing data will not be imputed. If a baseline value is missing, no change from baseline will be calculated.

Baseline is defined as the last observation prior to the administration of study medication.

SAS v9.4 or higher will be used for all analyses and a significance level of 0.05 will be used for all statistical tests.

Primary Analysis (Efficacy)

Primary analyses will be conducted across the two cohorts and by the two cohorts. Estimates will be presented with 95% confidence intervals.

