The primary efficacy endpoints will be summarized descriptively, across the two cohorts and by the two cohorts. A statistical test will not be performed on the Crude ACPR on Day 14. Achieving a rate of 80% will be the decision rule for cohort dose phase. For future study planning, a one-sample z-test will be used to compare the rate of success, as defined by the Crude ACPR on Day 14, to the hypothesized rate of 80%.

Secondary efficacy variables will be summarized descriptively (by cohort; on Days 0, 14, 42) with proportions, means, and medians. To inform future studies, all estimates will be presented with 95% confidence intervals ($1.96 \pm$ margin of error). Graphical summaries will be used to describe changes in efficacy endpoints over time.

Exploratory Analysis

Exploratory model-based analyses will be performed as data allows. These will include model-based analyses of PK, PD and PK/PD.

Safety Analysis

Adverse events (AEs) will be summarized in Listing 9: Cumulative Summary of Adverse Events. The listing will include the following information: Patient ID, AE Description, Start Date, Stop Date, Special Interest, Severity, Relationship to Study Drug, Action Taken, Outcome of AE, Expected AE, and if the AE was a Serious Adverse Event (SAE).

Laboratory values that fall outside a clinically accepted reference range must be evaluated and commented on by the Investigator and graded according to the DMID Toxicity Scale for Determining Severity of Adverse Events (Protocol Attachment 3, Section 8.1.2).

All related AEs, AEs with outcome death, AEs leading to permanent discontinuation of treatment, SAEs and related SAEs will be summarized in Listing 10: Cumulative Summary of Serious Adverse Events. The listing will include the following information: Patient ID, Age, Sex, Dose, SAE Description, Start Date, Stop Date, SAE Category, and Relationship to Study Drug.

Treatment related AEs are those rated by the Investigator as "definite", "probable", "possible". In case relationship is unknown or missing the worst case will be assumed and the AE will be considered to be drug related

Planned Interim Analyses

Interim analyses will be made to review parasite reduction, adverse events, and clinical laboratory data. Following review, a decision on cohort progression will be made. However, as this is an exploratory study no formal analyses with adjustments for type I error are planned.

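### SAP Section 4 ties the primary efficacy summary to two cohorts at 600 mg and 300 mg, but the design has up to three regimens and 300 mg appears only in the optional third

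*Combined protocol and SAP*

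**What the plan says.** SAP Section 4, General Approach, describes the design as follows: "The overall study design involves two cohorts receiving SJ733 doses (600 mg and 300 mg) with and without cobicistat (150 mg) as cohorts". Under Primary Analysis (Efficacy) it continues: "Primary analyses will be conducted across the two cohorts and by the two cohorts". Estimates are to carry 95% confidence intervals. The instruction is then repeated for the endpoint itself: "The primary efficacy endpoints will be summarized descriptively, across the two cohorts and by the two cohorts".

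Other parts of the documents describe a different structure.

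- SAP Section 2, Study Design, sets a minimum of one cohort and a larger upper limit, "with a maximum of 3 cohorts (60 patients; 3 dosing regimens; 2 arms; 10 patients per arm) being tested". After success in Cohort 1 it says that "two other dosing regimens, expected to yield reduced total exposures of SJ733, may be investigated".
- In the same section, Cohort 1 is 600 mg with cobicistat 150 mg. Cohort 2 tests whether cobicistat is needed. Cohort 3 is optional, is 300 mg with cobicistat 150 mg, and opens when Cohort 2 is safe but its crude ACPR is below 60%.
- The IRB application, Research Procedures, says "all cohorts will receive SJ733; cohorts 1 and 3 will also receive Cobicistat". Its Benefit vs. Risk section places the 300 mg combination in "the option to initiate a 3rd pair of cohorts, re-escalating SJ733 exposure".
- SAP Section 4, Sample Size Justification, says that primary analyses pool the two parasite arms within a dose cohort.
- SAP Section 5 provides every table, including Table 7 (Primary Endpoint), overall and by cohort.

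**The concern.** The description in Section 4 matches no state that the trial can reach under Section 2. If two regimens are run, they are Cohorts 1 and 2, and neither contains 300 mg. If 300 mg is run, there are three regimens, and Section 4 does not say which two it means. A trial that stops after one regimen is not covered either.

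This matters because a primary estimate with a confidence interval rests on the phrase. Even with the set settled, the pooled figure would average regimens chosen to differ in exposure: Section 2 expects roughly five-fold higher exposure in Cohort 1 than in Cohort 2, with Cohort 3 in between. The trial is meant to identify doses for Phase 2b, and a rate averaged over regimens belongs to none of them. It also sits badly with the rule in Sample Size Justification that pooling is over species within a dose.

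**Working it through.** **Step 1. The plan's own figure.** The power statement takes n = 20, a null rate of 80%, an alternative of 98% and one-sided 0.05. The critical proportion is 0.80 + 1.645 × √(0.80 × 0.20 / 20) = 0.947. Power is Φ((0.98 − 0.947) / √(0.98 × 0.02 / 20)) = 0.853, which reproduces the stated figure of at least 85%. The powered unit is thus one regimen with its two species arms pooled (2 × 10), not a set of regimens.

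**Step 2. The regimens.**

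| Cohort | SJ733 | Cobicistat | Status |
|---|---|---|---|
| 1 | 600 mg | 150 mg | always run |
| 2 | 600 mg (inferred) | none | after Cohort 1 success |
| 3 | 300 mg | 150 mg | optional, third |

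The Cohort 2 dose is an inference. Section 2 compares the Cohort 3 regimen with 600 mg alone and says that Cohort 3 would halve the SJ733 needed. The design figure is not available here. No regimen is 300 mg without cobicistat.

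**Step 3. Can the cohorts be species arms?** Elsewhere the SAP counts 2 to 6 cohorts of 10, which are species-by-dose groups. Section 4 does not use the word that way: it labels its cohorts by dose, it says that "summary statistics will be reported for observed data only, by dose cohort", and it pools species within dose.

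**Step 4. Candidate sets when three regimens exist.**

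- Cohorts 1 and 2: the core design, but no 300 mg.
- Cohorts 2 and 3: the only pair that has both doses and both boosted and unboosted patients, but it leaves out the starting regimen.
- All three: the natural reading of overall in Section 5, but not two cohorts.
- Cohorts 1 and 3: 600 mg and 300 mg, but everyone receives cobicistat, so it does not fit the sentence.

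**Step 5. How far the pooled rate depends on the set.** Assumptions: true ACPR 90%, 50% and 80% in Cohorts 1, 2 and 3; 10 patients per arm; no expansion; no reassignment between arms. From the progression rules, Cohort 1 must show at least 8/10 in each arm, and Cohort 3 opens in an arm after at most 5/10 in Cohort 2. The conditional binomial means per 10 patients are 9.17 for Cohort 1 (given ≥ 8), 4.01 for Cohort 2 (given ≤ 5), 6.63 for Cohort 2 in an arm that does not open Cohort 3 (given ≥ 6), and 8.00 for Cohort 3.

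| Set | Both arms open Cohort 3 | Exactly one arm opens it |
|---|---|---|
| 1 and 2 | (9.17 + 4.01)/20 = 66% | (18.33 + 4.01 + 6.63)/40 = 72% |
| 2 and 3 | (4.01 + 8.00)/20 = 60% | (4.01 + 6.63 + 8.00)/30 = 62% |
| All three | (9.17 + 4.01 + 8.00)/30 = 71% | (18.33 + 10.64 + 8.00)/50 = 74% |
| 1 and 3 (does not fit) | (9.17 + 8.00)/20 = 86% | (18.33 + 8.00)/30 = 88% |

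**Step 6. Does the choice move the figure across 80%?** By exact enumeration over the first three sets, the chance that any two lie on opposite sides of 80% is 1.2% if both arms open Cohort 3 and 12.4% if exactly one does. For a true Cohort 3 rate between 60% and 90% the ranges are 0–7% and 6–21%.

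**Step 7. Is a third regimen likely?** If both arms reach Cohort 2, the chance that at least one shows ≤ 5/10 is 1 − (1 − q)², where q is the binomial chance of ≤ 5/10. It is 86%, 60%, 28% and 6% for true Cohort 2 rates of 50%, 60%, 70% and 80%. The third regimen is a realistic path unless 600 mg alone works well.

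**The case against.** The strongest reply is that nothing depends on the cross-cohort figure. Success is judged per arm, progression uses counts out of 10, crude ACPR is not tested for any decision, and the per-regimen estimate is already specified and powered. All of this stands, and it limits the point to one descriptive estimate.

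A reader might infer that the pooled estimate is undefined once three cohorts exist. That is too strong. Section 5 supplies an overall column and per-cohort columns for any number of cohorts. What remains is ambiguity within Section 4 and a conflict with Section 5.

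A reader might also infer that the choice of set usually decides which side of 80% the figure falls on. On the same assumptions, Cohorts 1 and 2 against Cohorts 1 and 3 do split about 80% with chance 91% (both arms open) or 89% (one opens). But Cohorts 1 and 3 contain no patient without cobicistat, so the SAP sentence does not admit that pair. Among the other sets the chance is small, as Step 6 shows.

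Finally, SAP version 1.8 is dated 11/04/2022 and the stated start of analysis is 05/2021, which might suggest wording shaped by data. The documents do not support that. Reviews after each cohort explain an early start, and when the sentence was introduced cannot be seen. Enrolment was planned to close on 31 December 2021, so the two cohorts may simply be those that were run. The documents do not say, and under Section 2 the 300 mg label would still be wrong.

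**Conclusion.** The inconsistency is real and worth correcting, with limited effect. Section 4 misdescribes the regimens. With two regimens the error is in the label and does not change the set. With three, the primary efficacy summary is ambiguous and at odds with the table plan. In either case the cross-regimen rate is a poor primary estimate, because it averages regimens meant to differ in exposure.

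On the illustrative rates, the readings other than Cohorts 1 and 3 differ by about 11 percentage points (60% to 71%) when both arms open Cohort 3, and by about 12 (62% to 74%) when one does. These values rest on assumed true rates, no expansion, no reassignment between arms, and the rule that Cohort 3 follows a safe but ineffective Cohort 2. The sentence in Section 2 on two further regimens could be read as letting Cohort 3 follow success in Cohort 2. The numbers would then change, but 300 mg would still come third and the set would still be unnamed. Per-cohort estimates, progression decisions and the 85% power statement do not change.

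**What to change.** 1. In SAP Section 4, General Approach, replace the sentence on two cohorts with a list of up to three regimens: Cohort 1, SJ733 600 mg plus cobicistat 150 mg; Cohort 2, SJ733 600 mg alone (dose to be confirmed by the sponsor); optional Cohort 3, SJ733 300 mg plus cobicistat 150 mg. State that each has a P. falciparum and a P. vivax arm.
2. In both places under Primary Analysis (Efficacy), replace the instruction on two cohorts with this: primary efficacy is reported for each regimen opened, by species arm and pooled over species within regimen, and no primary efficacy estimate is pooled over regimens.
3. In Table 7, drop the overall column, or keep it labelled as all treated patients, descriptive, not a primary estimate. The other tables can keep theirs.

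The cost is text edits and at most one descriptive column. No new data are needed, and enrolment, the progression rule and the sample size stay as they are.
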